7.5.2 One month follow-up phone call for premenopausal subjects (day 60 ± 7)

1. Collection of last menstrual period for premenopausal participants.

8. CRITERIA FOR EVALUATION AND ENDPOINT DEFINITION

8.1 Primary Endpoint

[figure not shown]
The primary endpoint is the dermal tolerability and safety of ENX gel at two doses: 10 mg daily and 20 mg daily, using objective assessments as defined in the CTCAE criteria (Table 1), and skin photos before and after treatment.

Table 1 Modified CTCAE for assessing skin toxicity of endoxifen gel applied to the breast skin. These assessments will be made on the breast skin (application site).

	Grade 1	Grade 2	Grade 3
Dry Skin	No erythema or pruritus	With erythema or pruritus	With erythema and pruritus
Pain of Skin	Mild pain	Moderate pain	Severe pain
Photosensitivity	Painless erythema	Mild to moderate pain with erythema	Erythema with blistering
Pruritus	Mild, requiring topical intervention	Intense, with changes from scratching, oral intervention needed	Intense, constant, limiting ADL or sleep, oral steroids needed.
Rash maculopapular	Macules or papules <25% of treated area, with or without symptoms (pruritus, burning, tightness)	Macules or papules >25% of treated area, with or without symptoms (pruritus, burning, tightness), limiting instrumental ADL	Macules or papules > 25% of treated area, with or without symptoms (pruritus, burning, tightness), limiting self-care ADL
Urticaria	Asymptomatic or mild symptoms, not requiring therapy	Moderate; limited local therapy needed, limiting instrumental ADL	Urticarial lesions covering >30% of application area; oral or IV intervention needed

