11.1.3 Severity of AEs

11.1.3.1 Identify the AE using the CTCAE version 4.0. The CTCAE provides descriptive terminology (MedDRA lowest level term) and a grading scale for each AE listed. A copy of the CTCAE can be found at http://ctep.cancer.gov/protocolDevelopment/electronic applications/ctc.htm

AEs will be assessed according to the grade associated with the CTCAE term. AEs that do not have a corresponding CTCAE term will be assessed according to the general guidelines for grading used in the CTCAE v4.0. as stated below.

CTCAE v4.0 general severity guidelines:

Grade	Severity	Description
1	Mild	Mild; asymptomatic or mild symptoms; clinical or diagnostic observations only; intervention not indicated.
2	Moderate	Moderate; minimal, local or noninvasive intervention indicated; limiting age-appropriate instrumental activities of daily living (ADL)*.
3	Severe	Severe or medically significant but not immediately life-threatening; hospitalization or prolongation of hospitalization indicated; disabling; limiting self-care ADL**.
4	Life-threatening	Life-threatening consequences; urgent intervention indicated.
5	Fatal	Death related to AE.

ADL

- *Instrumental ADL refers to preparing meals, shopping for groceries or clothes, using the telephone, managing money, *etc*.
- **Self-care ADL refers to bathing, dressing and undressing, feeding self, using the toilet, taking medications, and not bedridden.

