13. STATISTICAL CONSIDERATIONS

13.1 Study Design/Description

We plan a randomized, double-blind, Phase I trial with a control arm and a treatment arm, with dose escalation from 10 mg ENX gel daily (5 mg per breast) to 20 mg daily (10 mg per breast). Dose-limiting toxicity is defined as the occurrence of Grade 2 or greater skin response for any of the CTCAE parameters listed in Table 1.

Cohorts 1 and 2 will be randomized 2:1 (ENX gel and placebo). Cohort 3 will consist only of actively treated subjects. We planned that the sample size may range up to 38, depending on the frequency of DLT, and how early in each cohort DLT was observed. After completion of Cohort 2 (with accrual of 12 subjects each in Cohort 1 and 2), we will now accrue 8 subjects in Cohort 3, with a final accrual of 32 subjects. All subjects who receive any study drug will be evaluable for the primary endpoint of dermal toxicity.

[figure not shown]
We choose a 2:1 randomized design with a placebo arm with each dose in *order to establish variability of measurements when no treatment is applied*, and yet to provide treatment to as many subjects as possible. Randomization is double blinded, and the gel used in the treatment and control groups has similar appearance, consistency, and chemical composition, except for the presence of ENX in the active gel. The study will employ intent to treat principles. Although formal statistical comparison will be limited by the small sample size (as can be the case for Phase I trials), the placebo group will be used to interpret subjective symptoms such as skin irritation or pruritis. Combining placebo groups will yield a total of n=8, thus providing standard error of the estimate of SD/sqrt(8) and 0.5/sqrt/(8).

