APPENDIX E

Please use the following suggested statements for participant communications.

For Email, Phone or Text Reminders during the first week (and subsequently if needed) please use the suggested statement:

"Hello my name is [insert name] from [site name/department], regarding NWU2017-09-01 TopEND research study. Please remember to apply your study gel and complete your participant diary. If you have any questions please call [insert name], Research Coordinator at (xxx) xxx-xxx."

For Phone Calls to assess compliance, toxicity, and changes in medication please use the suggested statements:

"Hello my name is **[insert name]**, Research Coordinator at (xxx) xxx-xxx from [site name/department]. I wanted to check in with you briefly about the NWU2017-09-01 TopEND study. Is this a good time to talk?"

If no: "When would be a better time for me to call you?"

If yes: "As part of your study follow up, I am calling you to briefly assess your study compliance and symptoms. Since we last spoke on <<date>>>, have you missed your study medication on any days?"

If yes: "How many days did you miss your study medication? On what dates did you miss your study medication?"

"Since we last spoke, have there been any changes to your current medications? For example, a change in dose, stopping a medication, or starting a new medication."

If yes: "Please tell me what has changed."

"Since we last spoke on <<date>>, have you noted any changes in the skin of your breast?"

If the participant reports yes, If the participant reports yes, then utilize the plain language guide below to ask more probing questions as needed.

Plain Language Guide for assessing skin application AEs

- 1. Is your breast skin dry from gel application? If yes, is it red or itchy?
- 2. Do you have pain on your breast skin? If yes, how severe?
- 3. Is your skin itchy from gel application? If yes, how severe? Are you taking any medicine for it?
- 4. Do you have rash on your breast skin? If yes, how big is the affected area? Are you taking any medicine for it? Can you please send us a picture of your rash?
- 5. Do you have hives on the breast skin where you have applied the gel? If yes, how big is the affected area? Are you taking any medicine for it?

[&]quot;Since we last spoke on <<date>>, have you experienced any other symptoms?

[&]quot;Please remember to apply your study gel and fill out the study diary. Thank you for your time."

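### Table 1 puts mild itch at Grade 1 under Pruritus but at Grade 2 or 3 when dryness is also recorded, and no rule says which row decides a DLT

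*Combined protocol and SAP*

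**What the plan says.** Section 8.1 makes dermal tolerability, graded by Table 1, the primary endpoint. Two of its rows matter here.

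- Dry Skin: Grade 1 is "No erythema or pruritus", Grade 2 is "With erythema or pruritus" and Grade 3 is "With erythema and pruritus".
- Pruritus: Grade 1 is "Mild, requiring topical intervention" and Grade 2 is "Intense, with changes from scratching, oral intervention needed". Grade 3 is reserved for constant, intense itch that interferes with activities or sleep and calls for oral steroids.

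Section 13.1 defines a DLT as "the occurrence of Grade 2 or greater skin response for any of the CTCAE parameters listed in Table 1". Sections 3.2.2 and 13.7 add two conditions that Section 13.1 omits: the reaction must persist for at least 48 hours where the gel was applied, and it must be judged at least possibly related to study drug. A DLT ends study gel for that woman (Section 5.6) and leads to unblinding after the medical monitor has been consulted (Sections 3.2.2 and 6.9).

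The primary analysis in Section 13.4 estimates the incidence of skin irritation by Table 1, with confidence intervals, at each dose and on placebo. It names no grade threshold.

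The telephone guide in Appendix E opens its skin probes with "Is your breast skin dry from gel application? If yes, is it red or itchy" and asks nothing about degree at that point. Its third question does ask how severe any itch is and whether it is being treated. Section 3.2.1 reports no DLT in Cohort 1 and one in Cohort 2.

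**The concern.** The Dry Skin row has no term for severity, area or function. It counts signs, whereas the Pruritus row grades how bad one of those signs is. A reaction that is both dry and itchy fits both rows, and the two can give different grades for the same itch. Because a DLT needs only one qualifying row, the Dry Skin row prevails by default, and the result depends on whether someone noted dryness beside the itch.

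At stake is the meaning of the Grade 2 or greater incidence and of the DLT count. Those figures are read as severity, but a woman with faint itch on dry skin can rank above a woman with worse itch on skin not recorded as dry. The grade also has a consequence for the woman, since a DLT stops her gel.

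**Working it through.** The plan states no figure that rests on this row, so there is nothing to reproduce. The check applies the two rows literally and then sizes one reclassified woman.

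**Step 1. Grade each combination of signs.** Inputs: the Dry Skin and Pruritus rows of Table 1. Itch is taken as mild and needing topical treatment, and redness as mild.

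| Signs recorded | Dry Skin row | Pruritus row | Reaches DLT grade? |
|---|---|---|---|
| Dryness only | 1 | none | No |
| Mild itch only | none | 1 | No |
| Dryness + mild itch | 2 | 1 | Yes |
| Dryness + mild redness | 2 | none | Yes |
| Dryness + mild itch + mild redness | 3 | 1 | Yes |

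If the itch is too slight to need topical treatment, it meets no grade in the Pruritus row, and the gap to Dry Skin Grade 2 widens.

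**Step 2. Apply the other DLT conditions.** The 48-hour and relatedness conditions test duration and cause. A mild reaction under daily gel can satisfy both, so the third to fifth lines of the table can be DLTs. Transient dryness with itch cannot.

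**Step 3. Any-grade incidence.** Dryness alone is already Grade 1, and so is mild itch needing topical treatment. A woman in the third to fifth lines therefore counts as irritated whichever row is used. The conflict changes her grade, not whether she is counted.

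**Step 4. Size of one woman in the Grade 2 or greater incidence.** Inputs: 8 active subjects per cohort (Section 3.2.1), and placebo groups of 4 + 4 = 8 combined (Section 13.1).

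- Active arm: 1/8 = 12.5 percentage points.
- Pooled placebo: 1/8 = 12.5 percentage points.
- If Cohorts 1 and 3, both at 10 mg daily, are pooled (the plan does not say), 8 + 8 = 16 and one woman is 1/16 = 6.25 points.

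Exact (Clopper-Pearson) 95% intervals with n = 8:

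- 0/8: upper limit 1 − 0.025^(1/8) = 0.369, so 0 to 37%
- 1/8: 0.3 to 53%
- 2/8: 3 to 65%

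One woman moves the point estimate a good deal, but neighbouring results have widely overlapping intervals.

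**Step 5. What the reported counts allow.** With 0 DLTs in Cohort 1 and 1 in Cohort 2, at most one counted DLT so far can owe its status to the Dry Skin row alone. Neither the row behind that DLT nor the woman's arm is given. Conversely, a dry, itchy reaction filed only under Pruritus would have been left out of the count. The documents do not say whether any was.

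**The case against.** The strongest defence is that the sensitivity is intended. Section 3.2.2 ties the Grade 2 threshold to the need for long-term tolerability, and a row that grades combined signs need not agree with one that grades a single symptom. This explains the choice of Grade 2 as the DLT cut-off. It does not explain two grades for one itch, and no text justifies this row or says which row governs.

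Several other points stand and limit the concern.

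- A reader might set Dry Skin Grade 3 against the general scale in Section 11.1.3, where Grade 3 is "Severe or medically significant but not immediately life-threatening", and call it a second contradiction. Section 11.1.3 applies that scale only to events without their own CTCAE term. Dry skin has its own graded row, so the conflict lies within Table 1. The Photosensitivity row, where painless redness is Grade 1, concerns a different event term and adds little.
- Appendix E already collects itch severity. Only redness lacks a severity prompt. Section 3.5.1 also provides for photographs graded centrally against Table 1 and for consultation on reported reactions. Photographs cannot show itch, however, and no written rule tells the grader how to choose between rows.
- A reader might infer that the comparison with placebo is spoiled. Cohorts 1 and 2 are randomised and double-blind and use one table for both arms, and Section 13.1 keeps placebo precisely to interpret irritation and itch. The documents do not support a claim of bias between arms.
- It is tempting to say that the alcohol in both gels (about 53% by weight) makes mild dry itch foreseeable in either arm. Section 6.2 reports application-site reactions in 0% of placebo women in a trial of a related gel. Section 2.3 calls that type of formulation similar, though the present gel has less alcohol and adds oleic acid. The frequency here is unknown.

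**Conclusion.** The point holds on the text. As written, a mild dry, itchy reaction that meets the duration and relatedness conditions is a DLT, while the same itch without recorded dryness is Grade 1. The effect is confined to the Grade 2 or greater incidence and the DLT count, at 12.5 points per woman in a group of 8.

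The conclusion assumes that redness and itch in the Dry Skin row mean any degree. That is the literal wording, and it fits a Pruritus row that itself treats mild itch as pruritus.

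Two stronger readings should be resisted. First, a reader might infer that this row produced the Cohort 2 DLT; no misgrading can be shown, because the row is not reported. Second, a reader might infer that it drove the dose chosen for Cohort 3. Section 3.2.1 attributes that decision to more skin irritation and no permeation advantage at the higher dose, taken although only one DLT had occurred, and it does not say that the irritation comparison used Grade 2 or greater counts.

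**What to change.** 1. The sponsor should reconcile the Dry Skin and Pruritus rows with each other and with the DLT definition in Sections 3.2.2, 13.1 and 13.7, and state which row governs when one reaction fits both. The choice of grading and of stopping threshold is the sponsor's, and none is proposed here.
2. For the 8 women of Cohort 3, record dryness, redness and itch as separate items, each with its severity. In Appendix E this mainly means adding a severity prompt for redness to the first question.
3. Keep incidence by grade under Table 1 as printed as the primary report. Add one supplementary tabulation by Table 1 row that shows how many Grade 2 or greater events, and how many DLTs, arise only from the Dry Skin row. For Cohorts 1 and 2, label it post hoc and limit it to what the adverse-event records support. Section 11.1.2 requires verbatim term, grade, attribution and dates, but photographs at Study Visit 1 were taken only where there was skin toxicity (Section 7.4.1).

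The cost is a wording change to a table printed in two places, a prompt in the telephone guide, a few case report form fields and one extra table. The downside is that some past events may be shown under two classifications, which the report would need to explain.

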8.2 Secondary Endpoints

Demonstrate dermal permeation of ENX gel is similar to ENX levels achieved with oral delivery (mean values of 5-6 ng/G breast tissue). The mastectomy will be bread-sliced as per usual pathology protocol. Drug concentration in non-tumor tissues will be measured at 5 different sites within each breast. The central slice (in line with the nipple, will be sampled as shown in Figure 2 Two additional slices will be sampled, half-way between the center and the periphery of the breast, medially and laterally. The mastectomy specimen will be collected at surgery; the PCF will be called by the OR nurse as soon as the specimen is removed; details are described in section 10.2.2. If skin is resected (i.e. if the procedure is not a nipple-sparing mastectomy), a skin sample will also be collected for dermatological pathology assessment. The drug assays will be performed by LC/MS-MS as in our previous study [36].

- 2. Plasma concentration of drug: (E) and (Z) isomers of N- desmethyl-4-hydroxytamoxifen (ENX) and 4-hydroxytamoxifen (4-OHT) to be performed by [name] using LC/MS/MS as published by us previously[16, 17]. Blood will be collected with anticoagulant K2-EDTA.
- 3. Plasma hormone levels for steroid hormones: estradiol, progesterone, dehydroepiandrosterone (DHEA), androstenedione and testosterone to be measured by LC/MS/MS using methods developed for prior studies by our group[45]. Blood will be collected with anticoagulant K2-EDTA.
- 4. *Plasma concentrations of IGF-1/IGFBP-3 and SHBG*: IGF-1 and its binding proteins IGFBP-3, and SHBG[16, 46] to be measured by ELISA assays at Northwestern University, Comprehensive Metabolic Core. Blood will be collected with anticoagulant K2-EDTA.
- 5. Plasma levels of coagulation cascade proteins: four blood coagulation protein assays [factor VIII, factor IX, von Willebrand factor (vWF), and Protein S] using plasma samples to be performed at Hemostasis Laboratory, Northwestern Memorial Hospital. Blood will be collected with anticoagulant citrate.

Table 2. Priority list of Biomarker analysis (FFPE tissue block , 15 sections, 4 micron each)				
1	1 H&E section for histology review (leading)			
2	2 sections for Ki67 IHC assay (including an extra for repeats)			
3	1 section for Progesterone Receptor IHC assay			
4	1 section for Estrogen Receptor IHC assay			
4	9 sections for macro-dissection and RNA extraction			
5	1 H&E section for histology review (trailing)			

lymph node, if available.

6. ENX-response endpoints in breast tissue samples: Ki67 labeling index, PR and ER expression, and expression of a panel of genes reported to change with ENX exposure, will be measured in breast tissue samples obtained at diagnostic core needle biopsy (CNB) performed prior to study entry, and compared to the measurements in post-therapy surgical

samples. Both Ki67 reduction and increase in PR expression are associated with tamoxifen response [47]. In addition, we will measure expression of genes selected from those modulated by 4-OHT [48] and those affected by ENX [26] in MCF7 breast cancer cells. Hawse et al., have reported that ENX treatment opposed the expression of 28 genes modulated by estradiol alone in MCF7 cell culture [26]. Of these, 12 genes were regulated by both 4-OHT and ENX but not by fulvestrant, and 6 genes were uniquely modulated by ENX but not by 4-OHT or fulvestrant. On the other hand, they also reported that ENX modulates 177 genes that are independent from its effect in opposing estrogen signaling, suggesting that the molecular mechanism of ENX actions differ from those of 4-OHT and fulvestrant [26]. Our recently opened 4-OHT gel study will provide an opportunity to compare gene expression profiles in response to ENX and 4-OHT in tumor samples. At the end of the intervention period, the mastectomy specimen will be sampled to obtain tissue for these measurements. We will use NanoString nCounter® assays (NanoString Inc., Seattle, CA) as a research platform to evaluate differential expression of 100 genes. We will include the 50 genes of the Prosigna Breast Cancer Prognostic Gene Signature Assay (formerly called the PAM50 test): 1) to define tumor subtypes (luminal A/B, Basal, etc.) of core biopsy

specimen (baseline), 2) to evaluate differential expression of proliferation genes (CENPF, ANLN, CDC20, CCNB1, CEP55, MYBL2, MKI67) by intervention. Additional 50 genes will be selected from genes commonly responding to both 4-OHT and ENX treatments as well as genes uniquely modulated by ENX not by 4-OHT in MCF7 cells as Howse et al. reported [26]. The Pathologist will mark the tumor area on the H&E slides for macro-dissection. [name] laboratory will perform macro-dissection and total RNA extraction RNA rom FFPE sections of diagnostic core biopsy block and therapeutic surgical block with purification kit (Qiagen or Roche kit). Total RNA quality and quantity will be measured by Qubit and Bioanalyzer analysis (NU genomics core). RNA samples will be stored at -80°C. The RNA samples (minimum 120 ng RNA aliquot per sample) will be shipped to NanoString headquarter (Seattle, CA) as one batch with dry ice. The mRNA gene expression profiling using 100 ng will be performed with NanoString nCounter® assays NanoString nCounter assay by NanoString company staff at NanoString headquarters.

7. Polymorphisms in tamoxifen metabolizing enzymes will not be assessed in the current study, but germline DNA will be banked for future pooled analyses of transdermally versus orally administered tamoxifen and metabolites relative to metabolic efficiency for oral tamoxifen. Subjects will be given the option to consent to this future study.

8.3 Off-Agent Criteria

Participants may stop taking study agent for the following reasons: completed the protocol-prescribed intervention, adverse event or serious adverse event, inadequate agent supply, noncompliance, concomitant medications, or medical contraindication. Participants will continue to be followed, if possible, for safety reasons and in order to collect endpoint data according to the schedule of events.

All participants included in the study who received agent may be assessed for response to intervention, Participants who complete less than 80% of the planned dose or did not take the last 3 required doses will be considered non-compliant and will not be evaluable for secondary endpoints; Participants that receive agent but withdraw without initiating treatment will be replaced and will not be followed or evaluable for DLTs.

8.4 Off-Study Criteria

Participants may go 'off-study' for the following reasons: the protocol intervention and any protocol-required follow-up period is completed, AE/SAE, lost to follow-up, non-compliance, concomitant medication, medical contraindication, withdraw consent, death, determination of ineligibility (including screen failure), pregnancy, participant withdrawal, or physician decision.

8.5 Study Termination

NCI, DCP as the study sponsor has the right to discontinue the study at any time.

9. CORRELATIVE/SPECIAL STUDIES

9.1 Rationale for Methodology Selection

The techniques for endpoint assessment, measurement of drugs, metabolites and drug effects have been established in prior studies[17, 36]. The current study will contribute to the current knowledge base by providing critical dermal safety, pharmacokinetic and pharmacodynamic data on a potentially more effective tamoxifen metabolite than the previously tested 4-OHT; and by providing preliminary data on the anti-tumor and anti-tumorigenic efficacy of ENX.

Breast Tissue and Plasma drug concentration: The following factors should be used to assess assay performance in human plasma and breast tissue matrices: selectivity, linearity, precision, accuracy, recovery and stability, following the FDA's Guidance for Industry: Bioanalytical Method Validation [U.S. Department of Health and Human Services, Food and Drug Administration, Center for Drug Evaluation and Research (CDER), Center for Veterinary Medicine (CVM), May 2001.] Assays of (E) and (Z) isomers of N- desmethyl-4-hydroxytamoxifen (ENX) and 4-hydroxytamoxifen (4-OHT) will be performed by [name] using LC/MS/MS as published by us previously[16] [17].

IHC for Ki67, estrogen receptor (ER), and progesterone receptor (PR) analysis: other methods for measurement of proliferation are available but Ki67 labeling index (KI67-LI) is the most validated and widely used method of measuring proliferation in short-term intervention studies, and also most suited to the small tissue samples that will be available for baseline assessment (i.e. core needle biopsies). IHC is also a well-established and reproducible technique for measurement of hormone receptors. Tamoxifen and ENX have demonstrated growth suppression of established ER+ mammary DCIS and invasive carcinoma in by reduction in Ki67 [36, 49] and high PR expression correlated to the effectiveness of adjuvant tamoxifen in premenopausal ER+ breast cancer patients[50, 51]. We have also considered whether or not to perform laser capture microdissection of tumor and benign breast tissue in order to exclude stroma, but decided against this since changes in stroma may also be pertinent and LCM greatly increases the cost and complexity of the studies.

Plasma hormone levels for steroid hormones: estradiol, progesterone, dehydroepiandrosterone (DHEA), androstenedione and testosterone to be measured by LC/MS/MS using methods developed for prior studies by our group [45]. These are detailed in the PK/Biomarker Supplement.

Plasma concentrations of IGF-1/IGFBP-3 and SHBG: IGF-1 and its binding proteins IGFBP-3, and SHBG [16, 46] to be measured by enzyme-linked immunosorbent assay (ELISA) assays at Northwestern University, Comprehensive Metabolic Core. ELISA kits will be purchased from R&D systems Inc. and performed using the manufacturer's protocols. These are detailed in the PK/Biomarker Supplement.

Plasma levels of coagulation cascade proteins: four blood coagulation protein assays [factor VIII, factor IX, von Willebrand factor (vWF), and Protein S] using plasma samples to be performed at Hemostasis Laboratory, Northwestern Memorial Hospital. These are detailed in the PK/Biomarker Supplement.

RNA expression assay: In addition, we will measure mRNA expression of a panel to be derived from existing data on gene expression changes induced by ENX and 4-OHT [26, 48], and modified according to the best data available at the time that the final set of tissues become available. We will use NanoString nCounter analysis (Nanostring Technologies, Seattle, WA); this is a well-established and reproducible technique for determination of differential mRNA expression. These are detailed in the PK/Biomarker Supplement.

Genotyping assay for drug metabolism enzyme polymorphism analysis: Genotyping assay is a well-established, robust and reproducible technique for determination of polymorphism of genes. [name] lab has successfully done genotyping assays for study of single nucleotide polymorphisms (SNP) of enzymes involved in steroid hormone biosynthesis (NCI06B1 NAF hormone study project). We have used TaqMan® SNP genotyping assay kits from the Life Technologies Inc. With 4.5 million SNP assays available, including 3.5 million HapMap SNPs, 70,000 cSNPs and 160,000 validated assays, TaqMan® SNP genotyping assays make it easy to perform human and mouse SNP genotyping studies with the precision of TaqMan® reagent-based chemistry.[52]

